examine cognitive function under a variable duration of LFS. We hypothesize that there will be a trend towards improvement in task performance under the LFS setting, measured through reaction time and error rates, and that this improvement will be stable or enhanced with sustained LFS. We hope to utilize these results to inform the design of a larger phase 2 efficacy study. Our specific aims are as follows:

- 1) To monitor the safety of LFS in the STN of patients with PD by examining the psychological, cognitive, and motor consequences of LFS
- 2) To determine the feasibility of utilizing low frequency DBS to improve cognition in patients with PD by examining if there is a trend toward improved executive function with LFS over high frequency stimulation (HFS) and no stimulation settings.
- 3) To further examine feasibility by determining if the differential effects of LFS versus HFS of the STN are long lasting in a small patient group.

At present, DBS stimulators are set at varying stimulation frequencies based on the acute effects of DBS on motor performance, with limited understanding of cognitive consequences. Understanding the effects of different stimulation frequencies on non- motor tasks will help elucidate the mechanism behind cognitive impairment in PD. If our hypotheses are correct it could lead to the development of new treatment plans that involve alternating between low and high frequency stimulator settings to optimize both motor and cognitive domains. Ultimately, focused treatment for cognition may slow the progression from mild cognitive impairment to dementia, improving real world functioning and quality of life.

5) Background

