The protected health information will not be reused or disclosed to any other person or entity, except as required by law, for authorized oversight of the research study, or for other research for which the use of disclosure of PHI for which an authorization or opportunity to agree or object is not required by 45 CFR 164.512. The research could not be practicably conducted without the waiver, and without access and use of the PHI for recruitment.

9) Compensation to the Subjects

Subjects will be compensated \$10 per session. If the patient decides not to participate in further sessions, they will still receive the compensation for the completed sessions. Travel expenses up to \$30 per patient will be provided if needed. The compensation will be in the form of a gift card and will be given at the time of the visit.

PROTOCOL TITLE: Safety and feasibility of using low frequency deep brain stimulation of the subthalamic nucleus to improve cognitive performance in patients with Parkinson's disease

10) Study Timelines

The duration of the study from subject enrollment of the first patient to final data analysis will be approximately two years. Each individual subject will participate in the study for a maximum of 2 months for a total of 3 on-site experimental sessions and one telephone call. The first on-site visit will occur within the month prior to their planned DBS placement surgery, following the pre-operative visit. The second and third on-site visits will occur within the fourth week after the DBS electrode placement surgery, 3-4 days apart. A telephone call will be made 24 hours prior to the third on-site session to obtain additional safety information (Figure 1). Each participant will remain in the study for approximately 2 months from the time of consent. Participation is on a voluntary basis and subjects will reserve the right to withdraw participation in the study at any point of time. We expect the duration to enroll all study subjects will be approximately 2 years based on the number of patients who meet the inclusion and exclusion criteria.

We expect to complete the study by July 2017. The data will be analyzed as individual patients complete the study with further analyses after data collection is complete.

11) Study Endpoints

1. Safety: Safety endpoints will be measured by neuropsychiatric, motor, and cognitive testing:

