without stimulation and will complete the BDI. Informers will complete the NPI. Subsequently, the stimulators will be turned on, and each patient will repeat cognitive testing under gamma frequency (~130 Hz) and theta frequency stimulation (~5 Hz). The order of stimulation will be randomized. Stimulation will occur for 5 minutes prior to and continuously throughout each task. Amplitude and pulse width will be set to 3 V and 120 microseconds accordingly (Laxton & Lozano 2013) or as tolerated by the patient, and will remain constant across sessions. We will wait 20 minutes between testing conditions to elicit about 75% of DBS effects (Temperli et al 2003). At the end of the experimental testing session, the stimulator will be turned off or set to LFS in preparation for the second experimental session.

The second on-site experimental testing session will assess the effects of continuous theta stimulation on cognitive function. Patients will repeat cognitive testing after 48 hours of continuous theta stimulation. This second on-site testing session will occur 3-5 days following the first experimental session. Two days prior to the testing session, patients' stimulators will be turned on to the theta frequency stimulation setting and patients will return home and engage in normal activities. After 48 hours they will return to the clinic and repeat cognitive testing with continuous theta frequency stimulation. The UPDRS, NPI, and BDI will also be performed at this time. At the end of the session, their stimulators will be turned off.

We will screen for psychological changes by telephone once during the 2 day stimulation period. The patient will complete the BDI and a relative or caregiver will complete the NPI over the phone.

The structure of the experimental sessions is shown in Figure 2 and Figure 3.

[figure not shown]

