If you specify a person by name, a change to that person will require prior approval by the IRB. If you specify people by role (e.g., coordinator, research assistant, co-investigator, or pharmacist), a change to that person will not require prior approval by the IRB, provided that person meets the qualifications described above to fulfill their roles.

- Principal Investigator: review of past literature, administration of cognitive tasks, reprogramming DBS generator, analysis of data, recruitment of patients, undergo IRB course(s) for clinical research
- Co-Investigator: administration of cognitive tasks, analysis of data, recruitment of patients, undergo IRB course(s) for clinical research
- Research assistants: administration of cognitive tasks, analysis of data, undergo IRB course(s) for clinical research

Describe other resources available to conduct the research: For example, as appropriate:

- *Justify the feasibility of recruiting the required number of suitable subjects within the agreed recruitment period. For example, how many potential subjects do you have access to? What percentage of those potential subjects do you need to recruit?*

We have access to all patients referred to neurosurgery for implantation of electrodes for intracranial depth electrode seizure monitoring.

- *Describe the time that you will devote to conducting and completing the research.*

3 years

- *Describe your facilities.*

We require the ACC clinic exam rooms or cognitive testing rooms in the UC Davis imaging center for cognitive testing and electrical stimulation.

- *Describe the availability of medical or psychological resources that subjects might need as a result of an anticipated consequences of the human research.*

PROTOCOL TITLE: Safety and feasibility of using low frequency deep brain stimulation of the subthalamic nucleus to improve cognitive performance in patients with Parkinson's disease

Patients will be provided the opportunity to discuss untoward events with the clinical team and any additional consultations medically indicated.

- *Describe your process to ensure that all persons assisting with the research are adequately informed about the protocol, the research procedures, and their duties and functions.*

Each member of the research team will undergo IRB course(s) for clinical research. Each member will be required to read the protocol.

25) Prior Approvals

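### The HFS/LFS order at the first experimental session is randomised but not masked, and one person may program, test and analyse, so expectation could bias the acute LFS-versus-HFS contrast; the listed staff could reduce this cheaply.

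*Combined protocol and SAP*

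**What the plan says.** All references are to the combined protocol and SAP.

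- **Roles (section 24, Resources Available).** The principal investigator's duties include "administration of cognitive tasks, reprogramming DBS generator, analysis of data". The next rows show who else could test: "Research assistants: administration of cognitive tasks, analysis of data". The co-investigator is likewise listed for testing and analysis. Reprogramming appears only in the principal investigator's row.
- **Protection of the comparison (section 12, Procedures Involved).** "The order of stimulation will be randomized". The legend of Figure 2 repeats this. No section describes masking of patient, tester, scorer or analyst, concealment of the order, or a rule that the programmer does not test. The coded identifiers in sections 14 and 29 protect privacy and do not hide the stimulation condition.
- **Expectation (section 4, Objectives).** "We hypothesize that there will be a trend towards improvement in task performance under the LFS setting". Sections 12 and 17 express the same expectation, and section 24 requires every team member to read the protocol.
- **Outcomes (section 12).** Stroop and N-back are computerised with key presses. FAS fluency is spoken, limited to one minute per letter, and counted. No one is named as its timer or scorer.
- **Flow of results (section 10, Study Timelines).** "The data will be analyzed as individual patients complete the study". Section 15 adds a review by the principal investigator and study members after each contact, and committee reviews after 4, 8, 12 and 20 patients. It counts the cognitive tests as safety data.

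**The concern.** Randomising the order balances practice and fatigue between the two stimulated conditions. It does nothing about an effect that travels with the frequency: a tester who knows LFS is on and expects it to help, or a patient who knows which setting is running and tries harder or less hard.

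The outcomes differ in exposure. For FAS, a person must judge and count spoken words, so knowledge of the setting could affect both encouragement and scoring. For Stroop and N-back the computer records the response, so the remaining route is effort and encouragement.

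Improved executive function under LFS relative to HFS and no stimulation is specific aim 2 (section 4). Section 11 says the results from 20 patients will inform whether a large effectiveness study is warranted. A spurious difference could start a trial that should not start, and a bias the other way could stop one that should.

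**Working it through.** **1. What the plan allows.** I set the staffing list in section 24 against the procedures in section 12 and the analyses in section 14. The list permits one person to program, test and analyse. The procedures do not assign these tasks to different people, and the analysis does not call for coded conditions. The list also shows that the tasks could be separated, because two roles can test and analyse without being listed for programming.

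**2. Sample size.** Section 7 gives 22 subjects, of whom 2 only try out the computerised test: 22 − 2 = 20, which agrees with the 20 patients stated elsewhere. Section 7 says the study is not powered for efficacy. There is no alpha, SD or effect size, and so no power figure to reproduce.

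**3. Illustration of how much a bias could matter.** Assumptions, none of them in the plan:
- a paired t-test of LFS minus HFS (scored so that positive favours LFS) on one outcome, n = 20, df = 19, two-sided alpha 0.05, critical value 2.093;
- no true effect;
- a constant bias towards LFS of b SDs of the paired difference.

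The test statistic is then noncentral t with noncentrality b × √20 = b × 4.472, and the chance of a significant result favouring LFS is P(T > 2.093).

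| b (assumed) | noncentrality | chance of a significant result favouring LFS |
|---|---|---|
| 0 | 0 | 2.5% |
| 0.1 | 0.447 | 6.2% |
| 0.2 | 0.894 | about 13% (0.1335) |
| 0.3 | 1.342 | about 25% (0.2465) |
| 0.5 | 2.236 | about 56% (0.5645) |

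**4. The opposite direction.** In the same set-up a true effect of about 0.66 SD gives 80% power. If expectation favoured HFS by 0.3 SD, the net shift would be 0.66 − 0.30 = 0.36 SD. Power would then lie between 24.65% (shift 0.3) and 39.69% (shift 0.4). A bias of this size could thus hide a real effect as well as create a false one.

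**The case against.** - **The staffing list is not an assignment.** Section 24 answers a template question about roles and qualifications. It does not say who does what at E1. This stands: the documents permit the overlap but do not require it. A reader might infer that the principal investigator will do all three tasks unmasked, or that the examiner times and scores FAS. Neither is stated.
- **Patients may not be told the setting.** Section 29 says each session is described beforehand, not that the active frequency is disclosed, and the consent forms are not in the public text. This stands as a limit: the point about patients is that the available text is silent.
- **The direction is not given.** The directional hypothesis is the investigators'. Patients awaiting treatment stimulation might favour HFS, which section 5 describes as very effective for motor symptoms. This stands, and it makes the bias unpredictable rather than harmless.
- **The illustration is not the planned analysis.** Section 14 plans ANOVAs over three settings for Stroop and N-back and names no test for fluency. This stands. The percentages show sensitivity and do not estimate the trial's error rate; one b would not apply equally to all three tests.
- **Ongoing review is a safety requirement.** This stands, and any coding of conditions must leave that review unmasked.
- **It is an unpowered phase 1 study.** This limits the severity but does not remove the point, because the cognitive result is meant to inform a larger trial.

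**Conclusion.** The concern holds as a design weakness of one comparison. The plan randomises the order of the two E1 frequencies, describes no masking, and permits one person to program, test and analyse. Expectation could therefore bias the acute LFS-versus-HFS contrast, chiefly in FAS and less in Stroop and N-back.

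The documents give no size for the bias. On the stated assumptions, 0.2 to 0.5 SD towards LFS would raise the chance of a significant result favouring LFS from 2.5% to between about 13% and 56%. The upper figure depends wholly on assuming 0.5 SD.

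Two stronger readings are not supported. The documents do not show that bias will occur or that it must favour LFS. Nor would splitting roles prevent it: staffing alone does not address patient expectation, and a patient may feel a setting. The point does not extend to the UPDRS, BDI or NPI endpoints. It is a change that should be made, with medium confidence, as a cheap improvement.

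**What to change.** For the two randomised E1 conditions:

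1. One team member programs the generator. A different member already listed for testing (co-investigator or research assistant), not told the setting, administers and scores the Stroop, N-back and FAS.
2. Tell patients that two settings will be tested in random order, without saying which is on.
3. Label the two conditions A and B in the file for the section 14 efficacy analysis, with the key held away from the analyst until those analyses are run.
4. State that the safety committee and those doing the per-visit safety review keep unmasked access to all data, including cognitive results by condition.
5. State that the no-stimulation and 48-hour LFS conditions are open-label. At E1 the no-stimulation test always comes first, and the 48-hour session is LFS by design.

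Asking tester and patient to guess the setting after each condition would show how well the masking worked.

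**Cost.** Two existing team members at E1 instead of possibly one, some scheduling, and protocol wording. Sample size, stimulation settings, visit schedule and safety reviews are unchanged. Masking may be incomplete if a setting is felt or visibly changes motor signs, so the claim in the protocol should be reduced bias. Label: cheap improvement.
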